6.6.1 Dose Modification for V937

The most common drug-related adverse reactions seen with V937 treatment continue to be fatigue, chills, pyrexia and influenza-like illness. These events are mainly Grade 1 or 2 in severity, transient, and easily managed.

In addition, a group of treatment-related AEs is specific to studies where V937 is delivered by ITu administration. This includes injection site pain, injection site erythema, injection site reaction, injection site pruritis, injection site discharge and injection site edema. These AEs are associated with the intralesional procedure, and have not been reported when V937 has been given by the IV or intravesicular route. These symptoms are limited to being mild (Grade 1) in severity.

As common practice, anti-inflammatory or anti-allergic agents, such as acetaminophen or ibuprofen, should be initiated if Grade 2 fever, chill, or site injection reaction occurs. Permanently discontinue V937 if these Grade 2 AEs reoccur in the same participants or are >Grade 2. For infusion reaction related to IV administered V937, please refer to [Table 10](#) for guidance. For other instances in which dose interruption(s) may be required, discuss with Sponsor.

Pembrolizumab treatment will be modified for the AEs described in Section 6.6.2.

6.6.2 Immune-Related Events and Dose Modification (Withhold, Treat, Discontinue)

Dose Modification and Toxicity Management for Immune-related AEs Associated with Pembrolizumab

AEs associated with pembrolizumab exposure may represent an immune-related response. These irAEs may occur shortly after the first dose or several months after the last dose of pembrolizumab treatment and may affect more than one body system simultaneously. Therefore, early recognition and initiation of treatment is critical to reduce complications. Based on existing clinical study data, most irAEs were reversible and could be managed with interruptions of pembrolizumab, administration of corticosteroids and/or other supportive care. For suspected irAEs, ensure adequate evaluation to confirm etiology or exclude other causes. Additional procedures or tests such as bronchoscopy, endoscopy, skin biopsy may be included as part of the evaluation.

Dose Modification and Toxicity Management Guidelines for irAEs associated with pembrolizumab monotherapy, coformulations, or IO combinations are provided in [Table 9](#).

Table 9 Dose Modification and Toxicity Management Guidelines for Immune-related Adverse Events Associated with Pembrolizumab Monotherapy, Coformulations or IO Combinations

General instructions: 1. Severe and life-threatening irAEs should be treated with IV corticosteroids followed by oral steroids. Other immunosuppressive treatment should begin if the irAEs are not controlled by corticosteroids. 2. Pembrolizumab monotherapy, coformulations or IO combinations must be permanently discontinued if the irAE does not resolve or the corticosteroid dose is not ≤ 10 mg/day within 12 weeks of the last treatment. 3. The corticosteroid taper should begin when the irAE is \leq Grade 1 and continue at least 4 weeks. 4. If pembrolizumab monotherapy, coformulations or IO combinations have been withheld, treatment may resume after the irAE decreased to \leq Grade 1 after corticosteroid taper.				
irAEs	Toxicity Grade (CTCAE v5.0)	Action With Pembrolizumab Monotherapy, Coformulations or IO Combinations	Corticosteroid and/or Other Therapies	Monitoring and Follow-up
Pneumonitis	Grade 2	Withhold	
 Administer corticosteroids (initial dose of 1 to 2 mg/kg prednisone or equivalent) followed by taper Add prophylactic antibiotics for opportunistic infections 	
 Monitor participants for signs and symptoms of pneumonitis Evaluate participants with suspected pneumonitis with radiographic imaging and initiate corticosteroid treatment
	Recurrent Grade 2, Grade 3 or 4	Permanently discontinue		

irAEs	Toxicity Grade (CTCAE v5.0)	Action With Pembrolizumab Monotherapy, Coformulations or IO Combinations	Corticosteroid and/or Other Therapies	Monitoring and Follow-up
Diarrhea/Colitis	Grade 2 or 3	Withhold	
 Administer corticosteroids (initial dose of 1 to 2 mg/kg prednisone or equivalent) followed by taper 	
 Monitor participants for signs and symptoms of enterocolitis (ie, diarrhea, abdominal pain, blood or mucus in stool with or without fever) and of bowel perforation (ie, peritoneal signs and ileus) Participants with \geqGrade 2 diarrhea suspecting colitis should consider GI consultation and performing endoscopy to rule out colitis Participants with diarrhea/colitis should be advised to drink liberal quantities of clear fluids. If sufficient oral fluid intake is not feasible, fluid and electrolytes should be substituted via IV infusion
	Recurrent Grade 3 or Grade 4	Permanently discontinue		
AST or ALT Elevation or Increased Bilirubin	Grade 2 ^a	Withhold	
 Administer corticosteroids (initial dose of 0.5 to 1 mg/kg prednisone or equivalent) followed by taper 	
 Monitor with liver function tests (consider weekly or more frequently until liver enzyme value returned to baseline or is stable)
	Grade 3 ^b or 4 ^c	Permanently discontinue	
 Administer corticosteroids (initial dose of 1 to 2 mg/kg prednisone or equivalent) followed by taper 	
T1DM or Hyperglycemia	New onset T1DM or Grade 3 or 4 hyperglycemia associated with evidence of β -cell failure	Withhold ^d	
 Initiate insulin replacement therapy for participants with T1DM Administer antihyperglycemic in participants with hyperglycemia 	
 Monitor participants for hyperglycemia or other signs and symptoms of diabetes

irAEs	Toxicity Grade (CTCAE v5.0)	Action With Pembrolizumab Monotherapy, Coformulations or IO Combinations	Corticosteroid and/or Other Therapies	Monitoring and Follow-up
Hypophysitis	Grade 2	Withhold	
 Administer corticosteroids and initiate hormonal replacements as clinically indicated 	
 Monitor for signs and symptoms of hypophysitis (including hypopituitarism and adrenal insufficiency)
	Grade 3 or 4	Withhold or permanently discontinue ^d		
Hyperthyroidism	Grade 2	Continue	
 Treat with nonselective beta-blockers (eg, propranolol) or thionamides as appropriate 	
 Monitor for signs and symptoms of thyroid disorders
	Grade 3 or 4	Withhold or permanently discontinue ^d		
Hypothyroidism	Grade 2, 3 or 4	Continue	
 Initiate thyroid replacement hormones (eg, levothyroxine or liothyronine) per standard of care 	
 Monitor for signs and symptoms of thyroid disorders
Nephritis: grading according to increased creatinine or acute kidney injury	Grade 2	Withhold	
 Administer corticosteroids (prednisone 1 to 2 mg/kg or equivalent) followed by taper 	
 Monitor changes of renal function
	Grade 3 or 4	Permanently discontinue		
Neurological Toxicities	Grade 2	Withhold	
 Based on severity of AE administer corticosteroids 	
 Ensure adequate evaluation to confirm etiology and/or exclude other causes
	Grade 3 or 4	Permanently discontinue		

irAEs	Toxicity Grade (CTCAE v5.0)	Action With Pembrolizumab Monotherapy, Coformulations or IO Combinations	Corticosteroid and/or Other Therapies	Monitoring and Follow-up
Myocarditis	Grade 1	Withhold	
 Based on severity of AE administer corticosteroids 	
 Ensure adequate evaluation to confirm etiology and/or exclude other causes
	Grade 2, 3 or 4	Permanently discontinue		
Exfoliative Dermatologic Conditions	Suspected SJS, TEN, or DRESS	Withhold	
 Based on severity of AE administer corticosteroids 	
 Ensure adequate evaluation to confirm etiology or exclude other causes
	Confirmed SJS, TEN, or DRESS	Permanently discontinue		
All Other irAEs	Persistent Grade 2	Withhold	
 Based on severity of AE administer corticosteroids 	
 Ensure adequate evaluation to confirm etiology or exclude other causes
	Grade 3	Withhold or discontinue based on the event ^e		
	Recurrent Grade 3 or Grade 4	Permanently discontinue		

irAEs	Toxicity Grade (CTCAE v5.0)	Action With Pembrolizumab Monotherapy, Coformulations or IO Combinations	Corticosteroid and/or Other Therapies	Monitoring and Follow-up

AE(s)=adverse event(s); ALT= alanine aminotransferase; AST=aspartate aminotransferase; CTCAE=Common Terminology Criteria for Adverse Events; DRESS=Drug Rash with Eosinophilia and Systemic Symptom; GI=gastrointestinal; IO=immuno-oncology; ir=immune related; IV=intravenous; SJS=Stevens-Johnson Syndrome; T1DM=type 1 diabetes mellitus; TEN=Toxic Epidermal Necrolysis; ULN=upper limit of normal.
 
Note: Non-irAE will be managed as appropriate, following clinical practice recommendations.
 
^a AST/ALT: >3.0 to 5.0 x ULN if baseline normal; >3.0 to 5.0 x baseline, if baseline abnormal; bilirubin:>1.5 to 3.0 x ULN if baseline normal; >1.5 to 3.0 x baseline if baseline abnormal
 
^b AST/ALT: >5.0 to 20.0 x ULN, if baseline normal; >5.0 to 20.0 x baseline, if baseline abnormal; bilirubin:>3.0 to 10.0 x ULN if baseline normal; >3.0 to 10.0 x baseline if baseline abnormal
 
^c AST/ALT: >20.0 x ULN, if baseline normal; >20.0 x baseline, if baseline abnormal; bilirubin: >10.0 x ULN if baseline normal; >10.0 x baseline if baseline abnormal
 
^d The decision to withhold or permanently discontinue pembrolizumab monotherapy, coformulations or IO combinations is at the discretion of the investigator or treating physician. If control achieved or ≤ Grade 2, pembrolizumab monotherapy, coformulations or IO combinations may be resumed.
 
^e Events that require discontinuation include, but are not limited to: encephalitis and other clinically important irAEs (eg, vasculitis and sclerosing cholangitis).
				

Dose Modification and Toxicity Management of Infusion Reactions Related to Pembrolizumab

Pembrolizumab may cause severe or life-threatening infusion-reactions including severe hypersensitivity or anaphylaxis. Signs and symptoms usually develop during or shortly after drug infusion and generally resolve completely within 24 hours of completion of infusion. Dose modification and toxicity management guidelines on pembrolizumab associated infusion reaction are provided in [Table 10](#). Life-threatening infusion reactions have not been observed with V937.

Table 10 Pembrolizumab and V937 Infusion Reaction Dose Modification and Treatment Guidelines

NCI CTCAE Grade	Treatment	Premedication at Subsequent Dosing
Grade 1 Mild reaction; infusion interruption not indicated; intervention not indicated	Increase monitoring of vital signs as medically indicated until the participant is deemed medically stable in the opinion of the investigator	None
Grade 2 Requires therapy or infusion interruption but responds promptly to symptomatic treatment (eg, antihistamines, NSAIDs, narcotics, IV fluids); prophylactic medications indicated for ≤ 24 hrs	
Stop Infusion
 
Additional appropriate medical therapy may include but is not limited to: IV fluids Antihistamines NSAIDs Acetaminophen Narcotics
 
Increase monitoring of vital signs as medically indicated until the participant is deemed medically stable in the opinion of the investigator.
 
If symptoms resolve within 1 hour of stopping drug infusion, the infusion may be restarted at 50% of the original infusion rate (eg, from 100 mL/hr to 50 mL/hr). Otherwise dosing will be held until symptoms resolve and the participant should be premedicated for the next scheduled dose.
 
Participants who develop Grade 2 toxicity despite adequate premedication should be permanently discontinued from further study drug intervention.
	
Participant may be premedicated 1.5 h (± 30 minutes) prior to infusion of study intervention with: Diphenhydramine 50 mg PO (or equivalent dose of antihistamine). Acetaminophen 500-1000 mg PO (or equivalent dose of analgesic).

NCI CTCAE Grade	Treatment	Premedication at Subsequent Dosing
Grades 3 or 4 Grade 3: Prolonged (ie, not rapidly responsive to symptomatic medication and/or brief interruption of infusion); recurrence of symptoms following initial improvement; hospitalization indicated for other clinical sequelae (eg, renal impairment, pulmonary infiltrates) Grade 4: Life-threatening; pressor or ventilatory support indicated	Stop Infusion. Additional appropriate medical therapy may include but is not limited to: Epinephrine** IV fluids Antihistamines NSAIDs Acetaminophen Narcotics Oxygen Pressors Corticosteroids Increase monitoring of vital signs as medically indicated until the participant is deemed medically stable in the opinion of the investigator. Hospitalization may be indicated. **In cases of anaphylaxis, epinephrine should be used immediately. Participant is permanently discontinued from further study drug intervention.	No subsequent dosing
Appropriate resuscitation equipment should be available at the bedside and a physician readily available during the period of drug administration. For further information, please refer to the Common Terminology Criteria for Adverse Events v5.0 (CTCAE) at http://ctep.cancer.gov		

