6.6.2 Dose Modification for Pembrolizumab

The following information provides additional irAEs and related details to what is stated in Table 9.

irAEs	Toxicity grade (CTCAE v5.0)	Action with pembrolizumab
Endocrinopathies	Grade 2 adrenal insufficiency and hypophysitis	Withhold treatment until controlled by hormone replacement
	Grades 3 or 4 adrenal insufficiency or symptomatic hypophysitis	Withhold until adverse reactions recover to Grades 0-1 ^a
	Type 1 diabetes associated with Grade ≥ 3 hyperglycemia (glucose >250 mg/dL or >13.9 mmol/L) or associated with ketoacidosis	For patients with Grade 3 or Grade 4 endocrinopathies that improved to Grade 2 or lower and are controlled with hormone replacement, if indicated, continuation of pembrolizumab may be considered after corticosteroid taper, if needed. Otherwise treatment should be discontinued.
	Hyperthyroidism Grade ≥ 3	
	Hypothyroidism	Hypothyroidism may be managed with replacement therapy without treatment interruption.

irAEs	Toxicity grade (CTCAE v5.0)	Action with pembrolizumab
Hepatitis	Grade 2 with aspartate aminotransferase (AST) or alanine aminotransferase (ALT) >3 to 5 times ULN or total bilirubin >1.5 to 3 times ULN	Withhold until adverse reactions recover to Grades 0-1 ^a
	Grade ≥3 with AST or ALT >5 times ULN or total bilirubin >3 times ULN	Permanently discontinue
	In case of liver metastasis with baseline Grade 2 elevation of AST or ALT, hepatitis with AST or ALT increases ≥50% and lasts ≥1week	Permanently discontinue
Skin reactions	Grade 3 or suspected Stevens-Johnson syndrome (SJS) or toxic epidermal necrolysis (TEN)	Withhold until adverse reactions recover to Grades 0-1 ^a
	Grade 4 or confirmed SJS or TEN	Permanently discontinue
^a If treatment-related toxicity does not resolve to Grades 0-1 within 12 weeks after last dose of pembrolizumab, or if corticosteroid dosing cannot be reduced to ≤10 mg prednisone or equivalent per day within 12 weeks, pembrolizumab should be permanently discontinued.		

Italy

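### Table 9 contradicts itself on restarting pembrolizumab after hypophysitis: a participant now at Grade 2 is held if the event began at Grade 2 but may be dosed if it began at Grade 3 or 4

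*Combined protocol and SAP*

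**What the plan says.** Table 9 (Section 6.6.2) opens with general instructions and then gives one row per immune-related event.

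- **Instruction 2 (12-week rule):** pembrolizumab "must be permanently discontinued if the irAE does not resolve or the corticosteroid dose is not" 10 mg/day or lower within 12 weeks of the last treatment.
- **Instruction 3 (taper):** "The corticosteroid taper should begin when the irAE is" Grade 1 or lower, and it runs for at least 4 weeks.
- **Instruction 4 (restart):** "If pembrolizumab monotherapy, coformulations or IO combinations have been withheld, treatment may resume after the irAE decreased to" Grade 1 or lower, after the taper. No exceptions are listed.
- **Hypophysitis row:** "Hypophysitis Grade 2 Withhold", with no footnote. Grade 3 or 4 is to be withheld or permanently discontinued, with footnote d.
- **Footnote d:** the decision to withhold or stop "is at the discretion of the investigator or treating physician. If control achieved or" Grade 2 or lower, treatment may be resumed. The footnote is also attached to the row for type 1 diabetes (T1DM) or hyperglycemia and to Grade 3 or 4 hyperthyroidism.
- **Myocarditis row:** "Myocarditis Grade 1 Withhold". Grade 2 and above is a permanent stop. Corticosteroids depend on severity, and there is no footnote.

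Appendix 7 (Section 10.7) adds text for France. For Grade 2 adrenal insufficiency and hypophysitis it reads "Withhold treatment until controlled by hormone replacement". For Grade 3 or 4 endocrinopathies, continuation may be considered if the event has improved to Grade 2 or lower and is also controlled with hormone replacement where indicated.

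**The concern.** A restart rule should tell the investigator what to do with the participant in front of them. For hypophysitis at a current Grade 2, Table 9 gives two answers, and the more permissive one goes to the participant who had the more severe event.

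All three arms receive pembrolizumab, and Section 6.6 requires it to be held as Table 9 indicates whichever drug is blamed. Section 7.1 makes a permanent stop under these guidelines mandatory and does not allow a discontinued participant to restart. Applying the wrong line can therefore either re-dose someone whom another line would hold, or end treatment irreversibly.

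There is a reporting consequence too. Discontinuing study intervention due to an adverse event is a secondary endpoint (Section 3). Interruption and discontinuation due to an adverse event are both Tier 2 summaries (Section 9.6.2). In an open-label study, rules that can be read in two ways make those summaries depend partly on which line the site applied.

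**Working it through.** No sample size, power or error rate is involved and the plan states no figure to reproduce. The check is a comparison of hold grades with restart grades.

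**Hypophysitis**

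| Grade at onset | Action in the row | Governing restart line | Restart grade | Status at a current Grade 2 |
|---|---|---|---|---|
| 2 | Withhold, no footnote | Instruction 4 | 1 or lower, after taper | Held |
| 3 or 4 | Withhold or stop, footnote d | Footnote d | Control achieved, or 2 or lower | May be dosed |

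1. The Grade 2 row has no restart condition of its own, so instruction 4 is the only line that applies.
2. Footnote d joins its two conditions with *or*. Grade 2 without control is enough.
3. The two rows therefore disagree at the same current grade, and the looser threshold follows the worse history.

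The other rows carrying footnote d do not share this conflict. Grade 2 hyperthyroidism is a continue row, so resuming at Grade 2 agrees with it. The T1DM/hyperglycemia row has no separate Grade 2 hold.

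**Instruction 2 against footnote d.** Instruction 2 says treatment must stop for good if the event has not resolved within 12 weeks. Footnote d says treatment may resume once control is achieved. T1DM is managed in its row with insulin replacement, so a participant can be controlled on replacement without the event having resolved. Table 9 does not define resolution and does not say whether footnote d is an exception to instruction 2.

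**French text.** For Grade 3 or 4 endocrinopathies it requires Grade 2 or lower *and* control where hormone replacement is indicated. Footnote d requires either one. The United Kingdom entries in Appendix 7 are marked as replacing the main text, whereas the French entry is described as adding to Table 9. A French site therefore holds both rules with no stated order of precedence.

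**Grade 1 myocarditis.** The hold grade is 1 and the restart range is Grade 1 or lower, so the grade limit is already met when the hold begins. The remaining conditions are that the event has decreased, that a taper has been completed, and that the 12-week rule is satisfied. Because corticosteroids depend on severity, a taper at Grade 1 is not certain. The point at which dosing may resume is therefore unclear.

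**The case against.** **A row-specific footnote overrides a general instruction.** This is the ordinary way to read a table, and it largely answers the tension between instruction 2 and footnote d, leaving a clarification to make. It does not answer the hypophysitis conflict, because footnote d is absent from the milder row and so cannot override anything there.

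**Both restart lines are permissive and footnote d leaves the decision to the physician.** True, and no line compels dosing. But discretion that permits dosing at a grade whose own row says withhold still leaves two answers for one state.

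**The difference may be deliberate.** Onset and recovery thresholds need not match. Nothing in Table 9 says that this one is intended.

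**The French wording is an announced supplement.** Section 1.3 says that country variations exist, so different wording is not in itself an error. What stands is the missing precedence.

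**Grade 1 myocarditis.** A reader might infer that Table 9 allows re-dosing with the triggering event unchanged. The text does not support that. Instruction 4 requires the event to have decreased, which for a Grade 1 event can be read as falling below Grade 1, and it adds the taper. Instruction 2 separately requires resolution within 12 weeks. These lines can be read together, so this is an unclear restart point and not a strict contradiction.

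**Little turns on it.** There are no safety hypotheses, the Tier 2 intervals are descriptive, and the study is closing. This lowers the priority. It does not remove the point, because transfer to the extension study depends on availability, and participants still on pembrolizumab here remain under Table 9.

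**Conclusion.** The hypophysitis contradiction holds on the text alone: Grade 2 is a hold under one line and permitted dosing under another, depending only on how severe the event was at onset. The 12-week rule, French precedence and Grade 1 myocarditis are secondary points of clarity.

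The size cannot be given. The documents report no rates for these events, and even an assumed incidence would not count those who reach the disputed state, such as a Grade 3 or 4 hypophysitis that has fallen to Grade 2. Enrolment may also fall short of 135. The number is probably small.

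A reader might go on to infer a bias between arms or an effect on the primary analysis. The documents show neither: Table 9 governs pembrolizumab in every arm, and no difference in how it would be applied is evident. What is at stake is patient safety in individual cases and the consistency of the interruption and discontinuation summaries, not ORR.

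**What to change.** Reconcile Table 9 general instructions 2 to 4, the Hypophysitis, T1DM and Myocarditis rows, footnote d, and the French text in Appendix 7. State which line takes precedence where a general instruction, a row footnote and a country supplement all apply. If the difference between the two hypophysitis rows is intended, say so in the table. Say also how the 12-week rule applies to rows with footnote d, and what marks the restart point for Grade 1 myocarditis. Which clinical rule to adopt is for the sponsor to decide.

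The cost is amendment wording in Table 9 and Appendix 7. Sample size, the analysis methods and data collection are unaffected.

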6.7 Intervention After the End of the Study

Due to discontinuation of V937-011, participants who have completed or discontinued V937 treatment and are only receiving pembrolizumab may be enrolled in a pembrolizumab extension study, if available, to continue pembrolizumab monotherapy for up to 35 cycles from first pembrolizumab dose on V937-011 and to be monitored per the extension study as appropriate.

6.8 Clinical Supplies Disclosure

This study is open-label; therefore, the participant, the study site personnel, the Sponsor, and/or designee are not blinded. Study intervention (name, strength, or potency) is included in the label text; random code/disclosure envelopes or lists are not provided.

